#### Vital Signs Specific Derivations

For Body Temperature (°C), conversions to oral route will be made as follows:

- Tympanic: +0.5°C
- Oral: No Adjustment
- $T(^{\circ}\text{C}) = (T(^{\circ}\text{F}) - 32) \times 5/9$ : degrees Celsius (°C), degrees Fahrenheit (°F)

#### Vital Signs Clinically Significant Abnormal Criteria

Clinically significant abnormal quantitative vital signs measurements will be identified in accordance with the following clinically significant abnormal criteria:

---

Document: \\ieedc-vnasc01\Biosdata\Archigen\SAIT101\YWA21301\Biostatistics\Documentation\SAP  
Author:

Version Number: V2.0  
Version Date: 13Feb2019

Template No: CS\_TP\_BS016 Revision 4  
Effective Date: 01Apr2016

Reference: CS\_WI\_BS005

**Table: Clinically Significant Abnormal Criteria of Vital Signs**

Variable	Unit	Visit	Low	High
Systolic blood pressure	mmHg	Baseline	< 90 mmHg	> 180 mmHg
		Post-baseline	≤ 90 mmHg AND change from baseline ≤ -20 mmHg	≥ 180 mmHg AND change from baseline ≥ 20 mmHg
Diastolic blood pressure	mmHg	Baseline	< 50 mmHg	> 110 mmHg
		Post-baseline	≤ 50 mmHg AND change from baseline ≤ -15 mmHg	≥ 105 mmHg AND change from baseline ≥ 15 mmHg
Pulse	beats/min	Baseline	< 50 beats/min	> 120 beats/min
		Post-baseline	≤ 50 beats/min AND change from baseline ≤ -15 beats/min	≥ 120 beats/min AND change from baseline ≥ 15 beats/min
Body temperature	°C	Baseline	< 35.0 °C	> 38.3 °C
		Post-baseline	≤ 35.0 °C AND change from baseline ≤ -1.1 °C	≥ 38.3 °C AND change from baseline ≥ 1.1 °C
Respiratory rate	breaths/min	Baseline	≤ 10 breaths/min	≥ 24 breaths/min
		Post-baseline	≤ 10 breaths/min	≥ 24 breaths/min
Weight	kg	Baseline	None	None
		Post-baseline	percentage change from baseline ≤ -7.0 %	percentage change from baseline ≥ 7.0 %

## 16.5. B CELL RECOVERY

B cell recovery is defined as “peripheral B cell counts that have returned to Baseline values or the lower limit of normal, whichever is lower”. The incidence of B cell recovery and CD19+ B cell count per patient will be summarized at each visit after Week 24 and overall by treatment groups. Listings for B cell recovery data and CD19+ B cell count by subject will be provided.

## 16.6. OTHER SAFETY ASSESSMENTS

The following observations will be provided for listing only:

- Abnormal physical examination
- Chest X-ray
- QuantiFERON Gold test
- Pregnancy test
- HBV testing
- Virology Screen test

## 17. Immunogenicity Outcomes

The immunogenicity analyses and comparison will be performed using the SAF.

Document: \\ieedc-vnasc01\Biosdata\Archigen\SAIT101\YWA21301\Biostatistics\Documentation\SAP  
 Author: Version Number: V2.0  
 Version Date: 13Feb2019

Template No: CS\_TP\_BS016 Revision 4 Reference: CS\_WI\_BS005  
 Effective Date: 01Apr2016

The incidence of Human anti-chimeric antibodies (HACA) and neutralizing antibody at Day 1 predose and at Weeks 1, 2, 4, 12, 16, 24, 36 and 52 will be summarized by treatment group and visit.

- Incidence (%)= number of subject with specific assessment result/ number of subject with available assessment results \* 100%

Overall positive of HACA and neutralizing antibody from Day 1 will be summarized. Patients with at least one positive result up to Week 24, 52 after Day 1 will be considered as overall positive; Otherwise, patient without any positive result up to Week 24, 52 after Day 1 will be considered as overall negative.

For the treatment difference among treatment groups listed below, the proportion, 95% CI for the proportion, proportion difference, standard deviation, and 95% CI for the proportion difference will be reported. The Wilson Score method will be used to calculate 95% CI.

- Response:
  - HACA positive
  - HACA negative
  - Neutralizing antibody positive
  - Neutralizing antibody negative
- Treatment groups:
  - Rituxan®- Rituxan® (reference group)
  - Rituxan®- SAIT101
  - SAIT101-SAIT101
  - MabThera®-MabThera®

Listings for immunogenicity assessment data by subject will be provided.

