### **2.3.4 Immunogenicity**

- Incidence of HACA and neutralizing antibody at Day 1 predose and at Week 1, 2, 4, 12, 16, 24, 36, and 52

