### **3.6.4 Immunogenicity Assessments**

Blood samples (approximately 5 to 8 mL) will be taken at the visits shown in (Table 2) to determine the incidence of HACA and neutralizing antibody (using validated analytical methods).

Blood immunogenicity samples will be collected on Day 1 of First course (prior to the start of the first infusion), and on Weeks 1, 2, 4, 12, 16, 24, 36, and 52 with date and time of sampling accurately recorded. Wherever possible immunogenicity blood samples will be taken at the same time as blood is drawn for other analyses to limit repeated venipuncture. Additionally, immunogenicity should be assessed when patients show signs or symptoms of immune-response-related adverse events.

Human anti-chimeric antibody will be detected in serum samples using validated analytical methods. Serum samples in which HACA are detected will be reflexed to a Neutralizing Antibody Assay to evaluate the effect of the HACA on the biological activity of rituximab. Full instructions for collection, labeling, storage, and shipment of samples are provided in the Laboratory Manual.

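### SAP 17: read literally, the by-visit neutralizing-antibody incidence is a share of HACA-positive patients, not an incidence among those tested

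*SAP*

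**What the plan says.** - **Endpoint.** Protocol 2.3.4 lists "Incidence of HACA and neutralizing antibody at Day 1 predose" and at later visits through Week 52. Neither that section nor Protocol 6.7 gives a denominator or limits neutralizing antibody to HACA-positive patients.
- **Assay flow.** Protocol 3.6.4: "Serum samples in which HACA are detected will be reflexed to a Neutralizing Antibody Assay". No other route to the neutralizing assay is described.
- **By-visit rule.** SAP 17 says HACA and neutralizing antibody "will be summarized by treatment group and visit", and gives one formula for both: "number of subject with specific assessment result/ number of subject with available assessment results", times 100%.
- **Missing data.** SAP 6.3 leaves missing data unimputed unless stated otherwise. SAP 17 has no rule that scores a HACA-negative sample as neutralizing-negative at a visit.
- **Overall rule.** The next paragraph of SAP 17 classifies patients to Week 24 and Week 52. One positive result makes a patient overall positive. "Otherwise, patient without any positive result up to Week 24, 52 after Day 1 will be considered as overall negative".
- **Comparison.** SAP 17 then asks for proportions, proportion differences and 95% CIs for HACA positive, HACA negative, neutralizing positive and neutralizing negative. It names four sequence groups with Rituxan-Rituxan as reference. "The immunogenicity analyses and comparison will be performed using the SAF" and "The Wilson Score method will be used to calculate 95% CI". It does not say whether these use by-visit results or overall status.

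**The concern.** A HACA-negative sample is never sent for neutralizing testing, so it has no neutralizing result. If the SAP formula is applied to the neutralizing assay as written, HACA-negative patients drop out of the denominator at each visit. What remains is the proportion of HACA-positive patients whose antibodies neutralize. That is a legitimate descriptive quantity, but it is not the incidence that the protocol names as an endpoint.

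HACA status is observed after randomization (apart from the Day 1 sample) and may differ between products. Conditioning on it takes the HACA rate out of the comparison. A product with several times as many neutralizing-positive patients looks the same as its comparator if the neutralizing share among HACA-positives is equal. Two products with equal neutralizing incidence look different if their HACA rates differ. The denominators also become small, so the intervals become wide.

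The overall rule has a separate, smaller problem. It defines negative as the absence of a positive result, so a patient with no evaluable post-dose sample is also counted as negative.

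**Working it through.** The documents state no immunogenicity rate, power or precision, so there is no plan figure to reproduce. The check is a reading of the text followed by an illustration with assumed counts.

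**Step 1: the denominator by HACA status at a visit**

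| Patient at the visit | HACA result | Neutralizing result | By-visit HACA denominator | By-visit neutralizing denominator, literal | Overall rule |
|---|---|---|---|---|---|
| HACA-positive | yes | yes (reflexed) | in | in | positive or negative by result |
| HACA-negative | yes | none | in | out | negative unless positive at another visit |
| No evaluable sample | none | none | out | out | negative unless positive at another visit |

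The second row is the by-visit defect. The third row is the weakness of the overall rule: a patient in that position at every post-dose visit is scored negative without having been assessed.

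**Step 2: formulas**

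- Literal by-visit incidence: neutralizing-positives / HACA-positives.
- All-tested incidence: neutralizing-positives / patients with a HACA result.
- Wilson limits (l, u) for p = x/n with z = 1.96: [p + z²/(2n) ± z·√(p(1−p)/n + z²/(4n²))] / (1 + z²/n).
- Difference d = p1 − p2, with a Wilson-based (Newcombe) interval: lower d − √[(p1−l1)² + (u2−p2)²], upper d + √[(u1−p1)² + (p2−l2)²].

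**Step 3: inputs**

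Group size 94 is the planned arm size in SAP 2.4, with everyone assumed tested. All HACA and neutralizing counts are assumptions.

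**Step 4: masking.** HACA-positive 30 vs 10, neutralizing-positive 15 vs 5.

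- Literal: 15/30 = 50.0% vs 5/10 = 50.0%; difference 0.0 points (−31.3 to 31.3).
- All tested: 15/94 = 16.0% (Wilson 9.9 to 24.7) vs 5/94 = 5.3% (2.3 to 11.9); difference 10.6 points. Lower limit 10.64 − √(6.04² + 6.53²) = 1.7. Upper limit 10.64 + √(8.71² + 3.03²) = 19.9.
- HACA itself: 30/94 vs 10/94; difference 21.3 points (9.7 to 32.3).

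**Step 5: false signal.** HACA-positive 10 vs 30, neutralizing-positive 8 vs 8.

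- Literal: 8/10 = 80.0% vs 8/30 = 26.7%; difference 53.3 points (17.6 to 72.3).
- All tested: 8/94 = 8.5% in both; difference 0.0 points (−8.5 to 8.5).

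**Step 6: the groups actually compared**

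SAP 17 compares sequence groups, not the three original arms. Only eligible Rituxan patients are re-randomized, 1:1 (SAP 2.4), so with an even split the Rituxan-Rituxan reference is at most about 94/2 = 47. At an assumed 10% HACA rate that leaves about 47 × 0.10 = 4.7, or 5 patients, in the literal denominator. If 3 of 5 were neutralizing-positive, the Wilson interval would run from 23% to 88%. Steps 4 and 5 show the direction of the distortion at arm size. They do not forecast the planned comparison.

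**The case against.** A reader might infer more than the documents support in three ways.

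**That all neutralizing-antibody reporting is conditional on HACA.** It is not. The overall status to Week 24 and Week 52 counts a patient without any positive result as negative, which keeps HACA-negative patients in the denominator. By-visit incidence and cumulative status are also different summaries, so their using different rules is not in itself a contradiction.

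**That the treatment differences and 95% CIs are affected.** The SAP does not say so. The comparison paragraph follows the overall-status paragraph, uses matching positive and negative categories, and names no visit. If it rests on overall status, the HACA-positive denominator does not enter it.

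**That a real product difference would go unseen.** HACA proportions are reported for the same groups, and all results are listed by subject. In the masking example the HACA difference of 21.3 points would be visible. At low rates the better denominator would not settle much either: about 3 vs 6 neutralizing-positives of 94 gives 3.2 points (−3.5 to 10.4).

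The formula also does not tie available results to an assay, so it could be read as patients with any immunogenicity result at the visit. The table templates mentioned in SAP 7 are not among the documents reviewed and may set the denominator.

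These points limit the reach of the concern and lower its severity. They do not remove it. The most direct application of one formula to each assay gives the HACA-positive denominator, and nothing in SAP 17 or 6.3 directs a programmer otherwise. If two readings are possible, two programmers can produce different tables. The HACA line beside it helps a reader to spot masking, but it does not stop a spurious neutralizing difference from being reported.

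**Conclusion.** The concern holds for the by-visit neutralizing-antibody line. Reflex testing, a denominator of available results and no imputation together make that line, read literally, a share of HACA-positive patients. On assumed counts at 94 tested per arm it can show 0.0 points where the all-tested difference is 10.6 (1.7 to 19.9), or 53.3 points where the all-tested difference is 0.0. Whether the between-group intervals inherit this depends on a choice that the SAP leaves open. The overall status is free of this defect but, as worded, takes in patients with no evaluable post-dose sample as negatives. The size of that effect cannot be judged from the documents.

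Severity is minor to moderate. Immunogenicity is a secondary objective, SAP 17 sets no margin or success rule, and no equivalence conclusion depends on it. The sizes above rest on invented HACA and neutralizing rates and on arm-sized groups that are larger than the Rituxan-Rituxan reference.

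**What to change.** In SAP 17:

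1. For by-visit neutralizing incidence, use as denominator the SAF patients with an evaluable HACA result at that visit, and score HACA-negative samples as neutralizing-negative.
2. Report the neutralizing share among HACA-positives as a separate descriptive line, labelled as such.
3. Restrict overall negative to patients with at least one evaluable post-dose sample in the window, and show the number without one.
4. State that the neutralizing proportion differences and 95% CIs use the all-tested denominator, and whether they are based on overall status or on by-visit results.

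The cost is SAP wording and table programming. No new samples, assays or visits are needed.

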- t On Day 1, Day 15 (Week 2), and Week 24: immunogenicity sample will be collected before start of infusion. Wherever possible immunogenicity blood samples will be taken at the same time as blood is drawn for other analyses to limit repeated venipuncture. Immunogenicity sampling is also taken when patients show signs or symptoms of immune-response-related adverse events.

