### **6.7 Immunogenicity Analysis**

Incidence of HACA and neutralizing antibody and summary of counts of antibodies per patient at prior first dose on Day 1 and at Week 1, 2, 4, 12, 16, 24, 36, and 52 will be summarized overall and by treatment group.

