#### 2.1.2. SECONDARY OBJECTIVE

The secondary objectives of the study are to compare the safety, additional PK, PD, efficacy, tolerability, and immunogenicity of SAIT101 versus MabThera® versus Rituxan® in patients with RA.

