### **4.4. SAFETY ANALYSIS SET [SAF]**

The Safety Analysis Set (SAF) consists of all RAN patients who received at least one dose of study drug during Part A or Part B. Subjects will be analyzed according to the treatment received. The SAF is used as the basis for all safety analyses up to Week 52.

---

Document:	\\ieedc-vnasc01\Biosdata\Archigen\SAIT101\YWA21301\Biostatistics\Documentation\SAP	Version Number:	V2.0
Author:		Version Date:	13Feb2019

Template No: CS\_TP\_BS016 Revision 4  
Effective Date: 01Apr2016

Reference: CS\_WI\_BS005

If there is any doubt whether a subject was treated or not, they will be assumed treated for the purposes of analysis.

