## 14. Pharmacodynamics Analysis

Part A and combination of Part A and B will be analyzed.

Serum/plasma levels of PD variables at the time points pre-defined in the study protocol will be measured by validated methods and used for the PD analyses.

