### 14.1. PHARMACODYNAMIC CONCENTRATION DATA

A listing of PD blood sample collection times and derived sampling time deviations will be provided.

Change from baseline PD variables will be calculated as (observed [measured] postdose value minus baseline value). Percent change from baseline will be calculated as (100 x change from baseline/baseline). Baseline is defined as the value observed on Day 1 (immediately before the start of the first infusion in Part A) or screening (for IgG, IgM, IgA).

Observed, change from baseline, and percent change from baseline in CD19+ B-cell counts, will be listed and summarized by study part, treatment, and scheduled visit using descriptive statistics (n, mean, SD, CV%, minimum, median, and maximum). Data from unscheduled visits will be listed but not summarized.

---

Document: \\ieedc-vnasc01\Biosdata\Archigen\SAIT101\YWA21301\Biostatistics\Documentation\SAP  
Author: Version Number: V2.0

Version Date: 13Feb2019

Template No: CS\_TP\_BS016 Revision 4  
Effective Date: 01Apr2016

Reference: CS\_WI\_BS005

Depletion of CD19+ B-cell counts (defined as a CD19+ B cell count below 20/ $\mu$ L) will be summarized with incidence by scheduled visit up to Week 52. Time to B-cell depletion (calculated as first time CD19+ B cell count below the limit of quantification (20 cells/ $\mu$ L) minus time of first dosing, rounded to nearest whole day) and duration of CD19+ B cell depletion (calculated as time of first return to non-depletion minus time of first depletion rounded to the nearest whole day) will be summarized for subjects in Part A. Time to B-Cell depletion will be summarized, and presented with Kaplan Meier curves and estimates of median depletion time with corresponding 95% CI. Duration thereof will be summarized only.

Observed and change from baseline in IgG, IgM, and IgA levels as well as CRP levels will be listed and summarized up to W24 CSR while for W52 CSR and onwards analysis, both initial first and second courses of study treatment groups will be considered using descriptive statistics described above.

Analyte CD19+ B cell count, IgG, IgM, IgA, and CRP data which fall below quantifiable concentrations will be set to zero for all summaries while missing values will be omitted.

Plots of serial mean and individual observed, change from baseline and percent change from baseline for CD19+ B-cell counts over time by treatment on linear scale will be provided: 1) up to Week 24; 2) from Week 24 to Week 52.

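### SAP 17 reports antibody differences only between two-course sequences, sets no time point for them, and gives one-course patients no group

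*SAP*

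**What the plan says.** **Windows and groups.** SAP 17 runs the immunogenicity analyses in the safety set. For overall status it says: "Patients with at least one positive result up to Week 24, 52 after Day 1 will be considered as overall positive". The next paragraph introduces the comparisons: "For the treatment difference among treatment groups listed below, the proportion, 95% CI for the proportion, proportion difference, standard deviation, and 95% CI" for the difference, by the Wilson score method. The groups are Rituxan-Rituxan (reference), Rituxan-SAIT101, SAIT101-SAIT101 and MabThera-MabThera. No Part A arm is listed and no week is attached to the differences. By-visit incidence is given by treatment group, without defining the group.

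**Timing of the sample.** Protocol Table 2, footnote t: "On Day 1, Day 15 (Week 2), and Week 24: immunogenicity sample will be collected before start of infusion".

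**Who gets a second course.** Protocol 3.6.1.3 makes retreatment depend on joint-count response at Week 24, and Protocol 3.2.3 adds neutrophil and platelet limits. Under SAP 2.4 only eligible Rituxan patients are re-randomised 1:1. Protocol 3.2.3 keeps ineligible patients in follow-up.

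**Grouping rules elsewhere.** SAP 4.4, on the safety set: "Subjects will be analyzed according to the treatment received". SAP 5 says that the final analysis takes both courses into account, but names no label for patients with one course. SAP 14, on pharmacodynamics: "Part A and combination of Part A and B will be analyzed". For immunoglobulins and CRP, SAP 14.1 says of the Week 52 report that "both initial first and second courses of study treatment groups will be considered using descriptive statistics described above"; its Week 24 part refers to a report that SAP 2.6 cancels.

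**Purpose.** A secondary objective (SAP 2.1.2) is to "compare the safety, additional PK, PD, efficacy, tolerability, and immunogenicity of SAIT101 versus MabThera" versus Rituxan. Protocol 6.7 asks only that antibody incidence "will be summarized overall and by treatment group".

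**The concern.** The Week 24 sample is drawn before any second-course infusion, so every scheduled antibody result up to that point reflects the Part A product alone. The second half of a sequence label cannot have caused it. What the label does carry is whether the patient responded by Week 24 and, for Rituxan patients, the outcome of a later re-randomisation. If Week 24 positivity is compared across these labels, a Part A outcome is grouped by a post-baseline event, and the Rituxan arm randomised on Day 1 is split.

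The labels also leave a gap. Patients with one course are in the safety set and give samples at Weeks 36 and 52, but none of the four groups describes them. One-course Rituxan patients were never re-randomised and fit neither Rituxan label as written.

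The stake is the comparison of SAIT101 with Rituxan. The Day 1 arms give its fullest randomised form up to Week 24, and the listed groups do not contain it.

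**Working it through.** **Arm size.** The plan needs 84 evaluable per group with 10% withdrawal: 84/(1 - 0.10) = 93.3, rounded up to 94, and 3 × 94 = 282. The stated figure reproduces.

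**Assumed inputs (none is in the documents).** All 94 per arm analysed; retreated share r = 0.5 (range 0.3 to 0.7); HACA rate p = 15% (range 5% to 30%), equal across products.

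**Formula.** Wald half-width = 1.96 × √[p(1-p)(1/n1 + 1/n2)], used because it shows how width scales with group size.

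**Day 1 arms, 94 v 94.** 1.96 × √[0.1275 × 0.02128] = 10.2 points (6.2 to 13.1 over the HACA range).

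**Reading 1: only retreated patients carry a label.**
- SAIT101-SAIT101 v Rituxan-Rituxan: n1 = 94r = 47, n2 = 94r/2 = 23.5. 1.96 × √[0.1275 × 0.06383] = 17.7 points (10.8 to 22.7 over the HACA range).
- Ratio to the Day 1 width = √[3/(2r)] = 1.73 (2.24 at r = 0.3, 1.46 at r = 0.7), whatever p is.
- SAIT101 v MabThera, 47 v 47: 14.4 points. Ratio √(1/r) = 1.41 (1.83 to 1.20).
- Rituxan-SAIT101 v Rituxan-Rituxan: this is the re-randomised comparison at its full size. It has no Day 1 counterpart and loses nothing.

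**Reading 2: one-course patients are folded into same-product labels.**
- SAIT101-SAIT101 v Rituxan-Rituxan: n1 = 94, n2 = 94(1 - r/2) = 70.5. Half-width 11.0 points (10.6 to 11.5 over the range of r).
- SAIT101 v MabThera remains the full Day 1 comparison, and the Rituxan arm can be rebuilt by adding its two columns.
- Possible bias with identical products, with a the HACA rate in retreated patients and b the rate in others: SAIT101 = b(1-r) + ar; Rituxan-Rituxan = [b(1-r) + ar/2]/(1 - r/2). With a = 20%, b = 10%, r = 0.5: 15.0% v 13.3%, a false difference of 1.7 points. Rituxan-SAIT101 (all retreated, 20%) v Rituxan-Rituxan: 6.7 points (8.2 at r = 0.3, 4.6 at r = 0.7). Exchanging a and b reverses the signs. With a = b both are zero.

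**Check with the SAP's type of interval.** Wilson-score limits for the difference at p = 15%, r = 0.5: Day 1 arms ±10.4 points; retreated only, SAIT101 v Rituxan-Rituxan, -20.6 to 15.9. The loss is of the same order.

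**The case against.** **No time point is stated.** The Week 24 and Week 52 windows sit in the paragraph on overall positivity, before the list of groups. Two-course labels also fit a Week 52 comparison in the single final report, and SAP 5 says both courses will be considered there. A reader might infer that the SAP prescribes Week 24 differences by sequence. The text does not go that far. It leaves that use open, because both windows are defined and nothing confines the differences to Week 52. SAP 5 does not settle the matter either, since it gives one-course patients no label.

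**The harms do not add up.** A reader might take it that every contrast loses precision, or that wider intervals and bias occur together. Neither is so. The switch contrast is untouched under Reading 1. The precision loss belongs to Reading 1 and the bias to Reading 2, and the two exclude each other. SAP 4.4 leans towards Reading 1 without stating a rule for sequences.

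**The stakes are limited.** SAP 2.6 presents these as added analyses. They have no margin, power claim or decision rule, and the incidence that Protocol 6.7 requires is reported in any case. By-visit incidence is not tied to the four sequences, so Part A columns are not excluded there. The table templates cited in SAP 7 are not available and may define further columns.

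These limits stand. What they leave is a section that, under either reading, lists no full Day 1 difference between SAIT101 and Rituxan, although SAP 14 shows that the plan separates Part A where it chooses to.

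**Conclusion.** The point holds as a gap in SAP 17 with a conditional cost. The differences have no time point, one-course patients have no group, and the Day 1 arms are not among the groups compared. If the differences are computed up to Week 24, the grouping is unsuitable for a Part A outcome. With only retreated patients labelled, the interval for SAIT101 v Rituxan-Rituxan is about 1.7 times as wide as the Day 1 interval (17.7 against 10.2 points). With one-course patients folded in, width barely changes (11.0 points), but contrasts with Rituxan-Rituxan may be distorted.

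The width ratio depends on the assumed retreated share; the widths in points also depend on the assumed HACA rate. The bias figures need antibody status to be related to retreatment, and no document shows such a link. The documents therefore do not support a claim that the planned comparison is biased. This is a modest but worthwhile correction to a descriptive analysis of a stated secondary objective.

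**What to change.** In SAP 17:

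- For HACA and neutralising antibody up to Week 24, report proportion differences with 95% CI by Part A arm in the safety set, for SAIT101 v MabThera, SAIT101 v Rituxan and MabThera v Rituxan.
- Keep the sequence groups for results after Week 24. Limit Rituxan-SAIT101 v Rituxan-Rituxan to re-randomised patients.
- State where one-course patients belong, and show them in separate columns by Part A product.
- Attach a time window to every difference.

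The cost is some SAP wording and a few table columns, with no new data. If the templates already do this, a sentence in SAP 17 saying so is enough.
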